2.2 Study Rationale and Hypothesis

Several studies have assessed the accuracy of transabdominal ultrasound in comparison with digital VE in determining fetal head position¹⁸⁻²¹. These have concluded that digital VE fails to identify the correct fetal head position in the majority of cases, especially at cervical dilatation $\leq 3-4\text{cm}$. Although transperineal ultrasound has been used pre-labour to predict the likelihood of PPROM patients going into labour²², its feasibility has not yet been assessed in the investigation and management of women either presenting with or established in labour. Initial studies have assessed head descent¹² and rotation²³ and angle of progression in labour^{13,24} to assess the second stage of labour to predict the likelihood of spontaneous vaginal delivery, instrumental delivery or Caesarean section. However, there have not been any studies directly assessing the feasibility of transperineal ultrasound scans.

We hypothesise that transperineal ultrasound will be a feasible and acceptable technique in comparison with digital vaginal examinations for 24-42 weeks gestation.

Using the data gathered in term patients, we will develop a model to predict pregnancy outcomes. This may aid in delivery of care to pregnant women by providing a real-time online calculation tool for the likelihood of vaginal delivery and length of labour based on repeat ultrasound measurements. This will allow a more

accurate prediction of the mode of delivery and reduce the number of vaginal examinations. This will improve the information available to women and their birth partners about the progress of their labour.

We anticipate improvements to women's health with additional information allowing better decision-making during labour enhancing the accurate recording of labour to a recordable skill. Universally, it may reduce the frequency of intrusive internal examinations and associated infection and will also be potentially useful in allowing the assessment of women in whom digital VE is traumatic or contra-indicated.

Overall, it may create a paradigm shift on delivery units in an area where the standard assessments have not changed in over one hundred years allowing better provision of resources.

3. Study Objectives

Primary objectives:

1. Feasibility of transperineal ultrasound scanning
2. Acceptability of transperineal ultrasound scanning
3. Creation of a "Sonopartogram" (Figure 3); an ultrasound based labour record

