4. Prediction model of time to delivery and mode of delivery at term
 - Caesarean section due to failure to progress and/or fetal distress

Secondary objectives:

1. Creation of a digital representation of the progress of labour (Figure 4).

4. Methodology and Design

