Transperineal ultrasound will then be carried out between gestations 24-42 weeks when a vaginal or speculum examination is otherwise also required to assess acceptability and feasibility. This scan will be done either immediately before or after the digital vaginal examination and the timing in relation the digital vaginal examination will be recorded.

Predictive Model:

In the predictive model group, there are no additional questionnaires. An admission ultrasound scan will be performed when the patient is deemed to be in established labour by the attending clinician. Subsequent scans will be performed as required at the time of routine clinical examinations typically between 2-4 hours apart.

The admission ultrasound scan will include if feasible fetal Doppler assessment of the umbilical artery, the cerebro-umbilical ratio (C/U: MCA/PI)¹⁶. Amniotic fluid index will also be measured. Fetal position will be assessed with a transabdominal scan and recorded as described above.

Dataset

Fixed variables

Maternal

Gestation

BMI, Age²⁸, Parity, Height, Ethnicity

Contraindication to vaginal examinations

Reason for avoidance of vaginal examinations

Fetal

EFW if known

Singleton

Multiple

Intrapartum

Non-USS:

Rupture of Membranes Yes/No: If Yes: Time

Spontaneous onset of labour Yes/No: If Yes: Time

Induction of Labour with prostaglandins Yes/No: If Yes: Time at insertion of prostaglandin

Syntocinon Yes/No: If Yes: Time
Epidural analgesia Yes/No: If Yes: Time

Modifiable parameters

USS Parameters: modified as labour progresses

- head position (TA ultrasound scan)
- cervical dilatation
- head-perineum distance
- caput
- moulding

Prolonged first stage of labour will be diagnosed according to national guidelines set in the UK by the National Institute of Health and Clinical Excellence (NICE) guidelines (cervical dilatation of < 2 cm in 4 hours)²⁵.

If recruited to the study, all patients will undergo normal clinical management with digital VEs or speculum examination performed as planned and in addition, ultrasound examinations before the digital VE/speculum by trained professionals. These ultrasound examinations will be blinded to the normal caregivers (midwives or doctors) so that they do not influence clinical management, though for practical reasons it will not be possible to blind the ultrasound operator to the clinical findings.

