4.14 External peer review

An earlier version of this protocol has been subject to external peer review by the British Medical Association leading to external funding (Helen Lawson Grant, awarded July 2014)

5. Study Outcome Measures

5.1 Primary measures:

1. Assessing feasibility of ultrasound by comparison with digital vaginal examinations:

- *Digital vaginal examination*: cervical dilatation, head station, caput, moulding, head position
- *Ultrasound*:
 - *Transabdominal Ultrasound*: Fetal head position
 - *Transperineal Ultrasound*: Cervical dilatation, head-perineum distance, caput and moulding

2. Acceptability of Transperineal Ultrasound to patients

3. Dataset for predictive model of outcome of labour of Caesarean section due to failure to progress and/or fetal distress

- Time to delivery

- Mode of delivery
- Primary indication for delivery
 - failure to progress
 - suspected fetal compromise

5.2 Secondary measures:

1. Neonatal outcome

- Gender
- Birth-weight
- Apgar Scores at 1 and 5 minutes
- Cord Gases
 - Fetal acidosis defined as arterial pH <7.10 and base excess >12.0mmol/l
- Neonatal unit admission within 24 hours
- Neonatal morbidity

6. Adverse events and reporting procedure

RISK ASSESSMENT - This study will not involve any risk to the participants. There are no predicted risks associated with the additional transabdominal and transperineal ultrasound scan. The scans will be used at the same settings and duration as routine ultrasound. We will be using probe covers and disinfection spray to clean the probe between patients.

The patient will be managed accordingly in concordance with local guidance and follow up arrangements will be made. The patient will still be followed up for the purposes of the study.

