A recent study by our group has shown that 95%¹⁵ of transperineal ultrasound parameters can be obtained compared to 82% of digital vaginal examination parameters¹⁵. With an alpha of 0.05 and a power of 90%, the minimum sample size required is 250 patients.

Labour prediction model

For the labour prediction model, there are approximately 15 variables with 10 patients needed per variable³²⁻³⁴ and an approximate 25% Caesarean section rate^{28,35,36} (the primary outcome) in the UK currently. This equates to 600 patients needed for the study.

Calculation:

$$15 \times 10 \times (100/25) = 600 \text{ patients}$$

As already discussed above, for statistical power and significance, a minimum of 42 and 250 patients is required for acceptability and feasibility respectively (24-42 weeks). For the predictive modelling, 600 patients are required (37-42 weeks).

The majority of the patients for the acceptability and feasibility samples will be recruited from the predictive modelling group (gestation 37-42 weeks). However, to allow sufficient data collection for feasibility, acceptability and development of the model, at least 700 patients will be required. As the trust has an annual delivery rate of 9000 annually, over a 24-month data collection period with a delivery rate of 18,000 across the trust, 700 patients (4%) sample size is achievable.

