7.1 Statistical and Data Analysis

In both groups, data will be collected prospectively and compared with vaginal examinations. In the second group, there will also be additional longitudinal measurements.

We will use a p value of <0.05 to indicate significance.

All measurements will be entered online at the time of examination to a secure database on the Imperial College Healthcare NHS Trust shared server where the patient will be identified by study number only. The database entry page will be accessible to investigators on their login, though they cannot interrogate data already entered. The data rules will follow closely to those performed through the recently completed multicentre European TRUFFLE study of fetal growth restriction where ultrasound measurements were captured at the time of examination³⁷.

For 24-42 weeks assessment of acceptability and feasibility:

Acceptability and preference will be tested using a questionnaire with Likert scale for discomfort, adapted from the W-DEQ Score³⁸

Feasibility of the ultrasound technique will be compared to digital VE for (a) total number of observations missing (head descent, position and cervical dilatation) during an admission on the delivery unit and (b) number of ultrasound examinations or digital VEs that could not be carried out for whatever reason where there was an intention to carry out a digital VE.

As a part of feasibility, *Reproducibility* between the *ultrasound and digital VE techniques* will be assessed both as a correlation (r) and agreement (using the Bland Altman method) between the ultrasound method and digital VE for head descent and cervical dilatation, and the Kappa statistic for head position.

Term predictive model:

The predictive value of intrapartum ultrasound parameters will be investigated using linear and logistic regression analyses. We will calculate the Receiver Operating Characteristic (ROC) curve with the Area Under the Curve (AUC) and associated positive and negative predictive values for delivery outcomes in the evaluation of transperineal ultrasound as a diagnostic tool.

8. Study supervision and Monitoring

Central and local supervision: the chief principal investigator at Imperial College London will be responsible for the protocol, quality control, interim analyses of the data, advice on progress and final analysis and reporting of the study. The Imperial Joint Research Compliance Office may audit the study as part of routine research governance.

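### The plan for the term prediction model reports AUC, PPV and NPV with no optimism correction and no calibration measure; figures taken from the development women would be too favourable

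*Combined protocol and SAP*

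**What the plan says.** Section 7.1 (Statistical and Data Analysis) covers the term predictive model in two sentences. The first gives the method: "The predictive value of intrapartum ultrasound parameters will be investigated using linear and logistic regression analyses". The second gives the performance measures: "We will calculate the Receiver Operating Characteristic (ROC) curve with the Area Under the Curve (AUC) and associated positive and negative predictive values". That second sentence goes on to tie these measures to delivery outcomes and to judging transperineal ultrasound as a diagnostic tool.

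Other sections bear on the point:

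- Section 3, primary objective 4, sets two targets: "Prediction model of time to delivery and mode of delivery at term".
- Section 5.1 lists as a primary measure: "Dataset for predictive model of outcome of labour of Caesarean section due to failure to progress and/or fetal distress".
- Section 7 (Labour prediction model) sizes the model on the basis that "there are approximately 15 variables with 10 patients needed per variable", with an approximate 25% Caesarean rate, giving 600 women.
- Section 4.9 lists five modifiable ultrasound parameters. At the admission scan it adds, where feasible, umbilical artery Doppler and the cerebro-umbilical ratio, and it adds the amniotic fluid index. On repetition it says: "Subsequent scans will be performed as required at the time of routine clinical examinations typically between 2-4 hours apart".
- Section 7.1 says of this group: "In the second group, there will also be additional longitudinal measurements".
- Section 2.2 foresees "a real-time online calculation tool for the likelihood of vaginal delivery and length of labour based on repeat ultrasound measurements".

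No section mentions bootstrap, cross-validation, a split sample, shrinkage or calibration. The only item described as validated is the questionnaire from which the study questionnaires are modified (section 4.9).

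**The concern.** A regression model fits its own data better than it fits new women, because the coefficients absorb part of the chance variation in the development sample. AUC, PPV, NPV and R-squared computed on that sample inherit the gain. Nothing in section 7.1 says that the gain will be removed.

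The second gap is calibration. AUC measures ranking only. PPV and NPV describe two groups either side of a cut-off. None of them shows whether a woman given a predicted risk of, say, 40% really has that risk. The tool foreseen in section 2.2 would give a likelihood, so this is the property that its user would rely on. An overfitted model gives risks that are too extreme, and without a calibration slope a reader of the results cannot see it.

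What is at stake is the reported performance of a primary objective and any later use of the tool. Clinical staff are blinded to the scan findings (sections 4.9 and 9.2), so conduct of the labours studied is not at issue.

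**Working it through.** **1. The plan's own figure.** Section 7: 15 × 10 × (100/25) = 600 women. Events: 600 × 0.25 = 150. Events per variable: 150/15 = 10. The figure reproduces.

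**2. Which variables are evaluated.** The text allows three counts:

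- about 15, the number used in section 7;
- eight ultrasound measures, if section 7.1 is read as ultrasound only: the five modifiable parameters (head position, cervical dilatation, head-perineum distance, caput, moulding) plus umbilical artery Doppler, cerebro-umbilical ratio and amniotic fluid index (5 + 3 = 8);
- five, if only the modifiable parameters enter.

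**3. Size of the optimism in AUC.** Optimism = AUC on the development women − AUC in new women. The documents give no expected AUC, so it is assumed. Simulation: 600 women, one record each, 25% events, independent normal predictors of which five truly predict, all variables entered, ideal AUC 0.75, performance then measured in new women.

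| Variables entered | AUC optimism | Calibration slope in new women (ideal 1) |
|---|---|---|
| 15 | 0.767 − 0.734 = 0.033 | 0.84 |
| 8 | about 0.02 (0.018) | not tabulated |
| 5 | 0.012 | 0.95 |
| 1 | 0.001 | 1.00 |

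Repeat runs gave 0.033 to 0.035 for 15 variables (slope 0.83 to 0.84) and 0.010 for five. With 15 variables, PPV in the top quarter of predicted risk is 52% on the development women against 48% in new women; NPV is 84% against 83%.

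**4. Sensitivity, 15 variables.**

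- Assumed ideal AUC of 0.65, 0.70 or 0.80: optimism 0.054, 0.042 or 0.026.
- Assumed event rate of 15%, 20%, 30% or 35%: optimism 0.046, 0.037, 0.031 or 0.028.

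**5. Time to delivery by linear regression.** With k predictors, n women and true R-squared ρ² (0.3 assumed):

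- Expected R-squared on the development women ≈ ρ² + (1 − ρ²)·k/(n − 1)
- Expected R-squared in new women ≈ 1 − (1 − ρ²)·(n + 1)(n − 2)/[n(n − k − 2)]

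k = 15: 0.3 + 0.7 × 15/599 = 0.318, and 1 − 0.7 × (601 × 598)/(600 × 583) = 0.281. Difference 0.037.

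k = 5: 0.3 + 0.7 × 5/599 = 0.306, and 1 − 0.7 × (601 × 598)/(600 × 593) = 0.293. Difference 0.013.

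**6. Does internal validation recover the bias?** With one record per woman, 15 variables and 25% events, a bootstrap that repeated the model fit gave a corrected AUC of 0.733 against a true 0.734 (uncorrected 0.765), and a slope of 0.84 against a true 0.83.

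**7. If several scans per woman are stacked as records.** Assumed: three scans per woman, within-woman correlation 0.5, 15 variables. True optimism is 0.038. Resampling scans finds 0.013; resampling women finds 0.032. At correlation 0.8 the figures are 0.032, 0.012 and 0.032.

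**The case against.** **Section 7.1 may evaluate ultrasound alone.** Its first sentence on the model speaks of ultrasound parameters and its second of ultrasound as a diagnostic tool. On that reading the overstatement is about 0.01 to 0.02, not 0.03. This stands. It is why the size is given as a range and why the first request is to name the variables. It does not supply a calibration measure on either reading.

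**The bias is small beside sampling error.** With 150 events, 450 non-events and an AUC of 0.75, the Hanley-McNeil standard error is √{[0.1875 + 149 × 0.0375 + 449 × 0.0804]/(150 × 450)} ≈ 0.025, a 95% half-width of about 0.05. The comparison is fair and keeps the point in proportion. But sampling error falls either way, whereas optimism always flatters the model, and a confidence interval around an uncorrected AUC does not remove it.

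**Ten events per variable already protects.** It limits overfitting but does not abolish it: the 15-variable result above is at exactly ten.

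**Resampling by woman may be irrelevant.** Section 4.9 defines a distinct admission scan. If only one record per woman is modelled, scans and women are the same unit. This stands, so that part of the fix is conditional.

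**This is a development study.** The timeline in section 4.9 plans development only, and section 2.2 says that the model may aid care. A reader might infer that the absence of external validation is a defect. The documents do not support that: putting the tool into use is not a step of this study. Internal validation belongs to development and needs no further women.

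**Conclusion.** The point holds as an omission with a predictable direction. As written, the measures in section 7.1 would be reported uncorrected and with nothing on calibration. If they are computed on the development women, the AUC would be too high by about 0.03 with 15 variables (slope about 0.84), about 0.02 with eight and about 0.01 with five. These sizes rest on assumptions that the documents do not supply: ideal AUC 0.75, independent predictors, all variables entered and one record per woman. They also use the plan's own 25% event rate. The direction does not depend on those values.

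Three stronger readings are not supported:

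- *That 0.03 is the established error.* It applies only if about 15 variables are entered, and section 7.1 does not say so.
- *That 600 women are too few because the 25% is a general Caesarean rate.* The arithmetic reproduces, and the documents do not show whether the rate in the model group is higher or lower, so no shortfall is shown.
- *That women in the study are put at risk.* Clinical staff are blinded to the scans.

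The change should be made: the model is a primary objective and the remedy is cheap.

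**What to change.** In section 7.1, name the variables that enter the evaluated model (the roughly 15 of section 7, or a stated list of ultrasound measures), and add text such as:

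> AUC, PPV and NPV will be reported after internal validation (bootstrap optimism correction, or cross-validation, repeating every modelling step), together with the calibration slope. If more than one scan per woman enters the model, resampling will be by woman. The cut-off for PPV and NPV will be fixed in advance or re-derived in each resample. R-squared of the linear time-to-delivery model will be corrected in the same way.

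Cost: a few sentences and a little more analysis work, on data already being collected; no extra participants. The reported AUC will be slightly lower, by about 0.01 to 0.03 depending on the variables entered.

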9.1 Ethical approval

The Study Coordination Centre will obtain ethics approval from the XXX Research Ethics Committee. The study also has been submitted for Site Specific Assessment (SSA) at Imperial College Healthcare Trust for local Trust Research and Development approval.

9.2 Consent

Consent to enter the study will be sought from each participant only after a full explanation has been given, an information leaflet offered and time allowed for consideration. Signed participant consent will be obtained. The patients GP will be informed of participation if the patient agrees. The right of the participant to refuse to participate without giving reasons will be respected.

After the participant has entered the study the clinician will be expected to manage the patient in exactly the same way that would have been expected had the participant not entered the study. The clinician will be blind to the information obtained from ultrasound assessment. All participants are free to withdraw at any time from the protocol treatment without giving reasons and without prejudicing further treatment.

9.3 Data Collection and Confidentiality

A study identification number anonymising all patient data will be used to collect and store data on an NHS computer software programme or database. The data may be transferred to a Third Party within the European Union but this will be an anonymised way with the use of study identification number only. This may be by an online website with secure access only. The Chief Investigator will preserve the confidentiality of participants taking part in the study and is registered under the Data Protection Act.

9.4 Data Storage and Archiving

All data will be stored for 10 years in accordance with the Imperial College data archiving policy.

9.5 Indemnity

Imperial College London holds negligent harm and non-negligent harm insurance policies, which apply to this study.

9.6 Sponsor

Imperial College London will act as the main sponsor for this study. Delegated responsibilities will be assigned to the NHS trusts taking part in this study.

